At every visit, participants are asked whether they are experiencing any symptoms. The onset, duration, quality, and severity of any symptoms are recorded on the *Symptoms Form* and tracked to resolution. If symptoms are severe, then the medical staff is notified immediately. These symptoms are also discussed at weekly team meetings to ascertain whether the symptoms meet criteria for an adverse event. If so, attribution and severity are also determined.

The hypothesis posed under **Specific Aim 1** (regarding efficacy and tolerability of GBP during and immediately following BUP detox) will be tested by comparing drug-screen results, withdrawal measures, craving, sleep quality and adverse events between GBP and placebo groups during weeks 2-3 and day 1 of week 4. The hypothesis posed under **Specific Aim 2** (regarding acceptability/feasibility of transition to NTX therapy) will be tested by determining retention, reasons for dropout, drug-screen results and side effects during the oral NTX induction (week 4) and depot NTX therapy (weeks 4-8). Queries posed under **Specific Aim 3** (regarding prognosticators) will determine whether salient factors such as sex, other drug use, dependence diagnoses, distress tolerance measures, caffeine use, etc.: **a)** differentially impact response to GBP vs. placebo on outcomes during detox, **b)** are associated with differential outcomes during transition to NTX and **c)** are associated with differential longer-term outcomes at week 16.

- J. Timeline. We estimate that we will develop standard operating procedures during months 1–3 and enroll 2-4 participants/month during months 4–53, allowing for major holidays and staff vacations. All study procedures will be completed by month 55 and follow-up interviews by Month 58. We will complete data analyses and manuscript preparation by Month 60. These data, if positive, will be used to support further research on adjunct GBP during BUP detox as well as provide preliminary feasibility data for outpatient transition to NTX therapy.

8. Data Analysis Methods:

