Statistical Analysis Plan

Study Title: Improving Treatment Outcomes for Prescription Opioid Dependence

NCT Number: NCT02543944

Date last reviewed by IRB: 10/4/2021

Data Analysis Methods:

We will compare baseline characteristics of the two groups using the intent-to-treat sample with analyses of variance for continuous variables (e.g., age) and Chi² analyses for categorical variables (e.g., sex, race) to determine whether any significant baseline differences have accrued despite randomization. In addition, given that later phases (i.e., transition, depot NTX therapy) may have different sample configurations due to anticipated dropout, we will similarly compare the two groups on participant characteristics. If we find significant baseline differences in variables within a phase or at each subsequent phase relative to the one prior, these differences will be informative of factors associated with treatment outcomes. For those variables found to affect outcome, we will use contingency tables with stratification or add these factors to the appropriate random regression models to adjust for these differences.

Our primary outcome is changes in opioid positive urines over time during the detox phase. Other major outcomes are: percentage of detox phase completers, naltrexone phase initiators and vivitrol receivers.

Specific Aim 1: Efficacy and tolerability of GBP versus Placebo during and immediately following BUP detox.

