For data during the BUP taper (weeks 2-3), dependent variables obtained at several time points (e.g., urine sample results for opioids, opioid withdrawal symptoms scores) will be entered into random regression models, also known as hierarchical linear models (HLMs), to determine whether scores change differentially across treatment groups [154, 155]. Continuous data will be analyzed longitudinally with MIXREG, an HLM modeling program for continuous measures [156]. Dichotomous urine results (i.e., negative or positive) will be analyzed longitudinally using the SAS procedure GLIMMIX, which allows an HLM modeling program for ordinal outcome measures [157]. We will use all available data in our analyses and will make no attempt to interpolate missing data. HLM methodologies fit a regression line for each participant, effectively interpolating missing data, before deriving final estimates. This approach of modeling repeated measures is specifically designed for use in repeated measures designs with missing data, allowing for intra-participant serial correlation and unequal variance and covariance structures over time. These problems, common to clinical trial data, are solved by incorporating available trend data for each individual with information on the behavior of the group from which the participant is drawn. If there are any significant baseline differences, the variable will be added as a cofactor in the HLM analyses. We will examine differences in retention using Kaplan-Meier Survival Analysis. Analyses will be done on those who participated long enough to start the BUP taper, as well as during GBP induction to detect possible differential dropout before the taper. To determine whether treatment group differences occurred in 1) success of retention from the BUP detox to the NTX transition and 2) eligibility to undergo oral NTX induction, we will build 2 X 2 contingency tables using percentages of participants in the GBP vs. placebo groups who 1) return on day 1 of week 4 versus drop out after completing the taper, and 2) test negative versus positive for opioids. The type, severity, and frequency of adverse events will be compared across groups. All analyses will employ a significance level of $\alpha = 0.05$, and all tests are two-tailed.

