scores, etc.). We will evaluate general predictors of successful outcomes (with success as defined above) regardless of treatment type and predictors of differential response to treatments. Depending on the distribution of participants with moderate versus severe opioid dependence, severity of opioid dependence will also be examined as a prognosticator. Our basic analytic strategy will be to dichotomize groups into the presence and absence of a dichotomous predictor variable (e.g., female or alcohol dependence diagnosis) and then to examine the relative predictive values on treatment outcomes by adding each factor to the log linear analyses for single time point outcomes and HLM for longitudinal measures such as frequency of self-reported drug use, opioid-negative urines and craving measures. Each continuous measure (e.g., HAM-A, distress tolerance scores) will be entered as a covariate in the above analyses.

Longer-Term Outcomes. Continuous data from the 16-week follow-up interview will be initially entered into repeated measures ANOVA's with group (GBP vs. placebo), successful completion of detox (yes vs. no), successful induction onto oral NTX therapy (yes vs. no), and successful transition to depot NTX therapy (yes vs. no) as factors. Dichotomous follow-up data will be entered into Chi² tables for each phase. Longitudinal data captured during each phase of the study and at follow-up will be entered into random regression models as above, and piece-wise comparisons will be made between each phase. For all analyses, a p value <0.05 will be used to infer statistical significance.

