Sample Size. PASS (Power Analysis & Sample Size) Software was used to estimate power. Sample size for the intent-to-treat sample was determined based on having enough power during and immediately following the BUP taper to detect group differences in the primary outcome of illicit drug use and identify potential prognosticators. Based on the proportion of participants in the GBP versus placebo groups having opioid-free urines on the last day of the BUP taper from our pilot trial with GBP [31, 129], treating the one missing value as positive, a difference in the percentage of participants with opioid-free urines at the end of detox as well as immediately prior to initiating NTX therapy will be detected with >90% power with an analysis sample size of 106 total participants anticipated to remain for NTX transition. Thus, our sample size is adequate to detect differences for our primary outcome during and immediately following the detoxification. Meanwhile, there has been minimal, if any, study of sex (or other bivariate prognosticator) differences for the effect of an adjunct medication for opioid dependence, much less for prescription opioid dependence. This study will provide unique data to quantify a potential difference. Given our expected sample size of 150 participants entering the BUP detox phase, the study will have >80% power for an effect size of 0.29 (small effect size), and 106 participants eligible for NTX transition will have >80% power to detect an effect size of 0.35 (considered a "medium" effect size).

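### Does the Sample Size paragraph overstate the power to find sex or other two-level differences in the gabapentin effect?

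*SAP*

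**What the plan says.** The Sample Size paragraph is the same in the SAP and in Protocol section 8. It says the sample was chosen "to detect group differences in the primary outcome of illicit drug use and identify potential prognosticators". It deals first with the comparison of GBP and placebo on opioid-free urines and concludes that the sample is adequate for it. It then remarks that there has been little study of "sex (or other bivariate prognosticator) differences for the effect of an adjunct medication for opioid dependence" and that this trial will supply data for putting a number on any such difference. Two power statements follow. The first concerns everyone who enters detox, 150 in number: "the study will have >80% power for an effect size of 0.29 (small effect size". The second concerns the smaller group expected to reach the naltrexone stage, and its effect is labelled medium: "106 participants eligible for NTX transition will have >80% power to detect an effect size of 0.35".

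Other sections bear on how to read this:

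- SAP, Specific Aim 3, covers predictors "regardless of treatment type and predictors of differential response to treatments", so it includes both main effects of a prognosticator and treatment-by-prognosticator differences. It names log-linear analysis for single time points and HLM for repeated measures.
- Protocol section 7.I asks whether factors such as sex "differentially impact response to GBP vs. placebo on outcomes during detox".
- SAP, Data Analysis Methods: "Our primary outcome is changes in opioid positive urines over time during the detox phase". The Aim 1 models are meant "to determine whether scores change differentially across treatment groups".

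**The concern.** The sentence just before the two power figures is about differences in a drug effect between the sexes, which is a treatment-by-factor interaction. A reader going straight on could conclude that the trial has more than 80% power to detect a small or medium interaction. Interactions are costly: with even splits, the standard error of a difference between two subgroup effects is twice that of the overall effect. If 0.29 and 0.35 are SD differences, the claim would be far too favourable, and a null sex-by-GBP result might be taken as evidence that the drug works alike in men and women when the trial could not have told. Aim 3 is a named aim judged at p<0.05, so that misreading would matter.

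**Working it through.** **Inputs from the documents.** N=150 with 0.29; N=106 with 0.35; stated power above 80%; two-sided 0.05.

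**Assumptions, not in the documents.** 1:1 allocation, an evenly split prognosticator, complete data. For longitudinal calculations, also equal spacing, a linear trend and exchangeable within-person correlation ρ.

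**1. Can the stated figure be reproduced?** No single basis is given, so several were tried. Results are for N=150 / N=106.

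- *w, 1 df.* Noncentrality is N·w²: 150 × 0.29² = 12.615 and 106 × 0.35² = 12.985. Square roots are 3.552 and 3.603. Power is Φ(3.552 − 1.960) = 94.4% and Φ(3.603 − 1.960) = 95.0%.
- *f, 1 df.* Same noncentrality, noncentral F: 94.2% / 94.6%.
- *r, Fisher z.* atanh(r)·√(N − 3) = 3.620 / 3.709: 95.2% / 96.0%.
- *4 df.* w: 82.4% / 83.7%. f: 81.0% / 81.7%.
- *Cohen's d, two equal groups, one measurement.* d·√(N/4) = 1.776 / 1.802: 42.7% / 43.7% (t-test 42.3% / 43.1%).

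So more than 80% holds on w, f and r at 1 df, and on w and f at 4 df. It fails on a single-measurement d.

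**2. Interaction as an SD difference at one time point.** The standard error is √(16/N) = 0.327 / 0.389 SD. The ratios are 0.29/0.327 = 0.888 and 0.35/0.389 = 0.901, giving power of 14.4% / 14.7% (14.3% / 14.5% by t). For 80% power the difference must be 2.80 × SE = 0.91 / 1.09 SD.

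**3. Interaction in change over time.** With six measures, the SD of one person's fitted first-to-last change is 5·√((1 − ρ)/17.5). Multiplying by √(16/N) gives the standard error. Power:

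| ρ | N=150, 0.29 SD | N=106, 0.35 SD |
|---|---|---|
| 0 | 11.5% | 11.7% |
| 0.5 | 18.3% | 18.7% |
| 0.8 | 38.3% | 39.2% |
| 0.9 | 65.1% | 66.4% |
| 0.95 | 91.3% | 92.1% |

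Power crosses 80% at ρ = 0.930 / 0.928. That threshold belongs to the assumed model: going from nine visits to two moves it between about 0.90 and 0.95. If correlation instead decays with the gap between visits (first-order autoregressive), a lag-1 value of 0.95 gives only about 25% power for the same fitted trend. These figures are also for a continuous outcome, whereas the urine result is dichotomous.

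**4. Interaction on the scales where the stated figure holds.**

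- *f.* With four equal cells, f = δ/4 for a difference δ in GBP effect. Then 0.29 and 0.35 mean 4 × 0.29 = 1.16 SD and 4 × 0.35 = 1.40 SD, with 94.2% / 94.6% power.
- *w.* A 1-df log-linear interaction has the noncentrality of step 1, hence 94.4% / 95.0% power. For a binary outcome near 50% with equal cells, w = δ/2, so the implied differences are 58 and 70 percentage points.

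On the usual conventions for w and r, medium starts at 0.3. The value labelled small, 0.29, lies just below that cut and the value labelled medium, 0.35, just above it.

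**The case for a change.** The strongest case for a change is that no reading gives what a casual reader would take from the paragraph. On d at one time point the power is wrong even for the main effect. On f the power is right, but small and medium would then describe sex differences of 1.16 and 1.40 SD. As main effects on w or r, the figures do not answer the question raised just before them. A sentence naming the scale and contrast would cost almost nothing.

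Part of this stands. The paragraph does not say what was computed, so its figures cannot be verified from the documents, and they should not be cited as power for moderator differences in SD units. It also stands that the trial has little power for modest moderator effects; even on w, the detectable differences are very large in absolute terms.

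It does not show an error. The link from the power figures to the interaction is inferred from their position. The sentence in between promises an estimate, not a powered test, and both the paragraph's stated purpose and Aim 3 include general prognosticators, which are main effects. The objection about labels applies to f but not to w, where the labels agree with convention even for an interaction. The 14-15% and the 0.93 each require a scale and a contrast, and the 0.93 also a visit count and correlation structure, that the documents never state.

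**Conclusion.** No change to the plan is needed. The figures of more than 80% for 0.29 and 0.35 hold on w, f or r (94-96% at 1 df; 81-84% at 4 df for w and f) and for a 1-df interaction on w or f (94-95%). They fail on a single-measurement d (42-44%) and on a subgroup difference in SD units at one time point (14-15%), but the documents adopt neither scale. At least one coherent reading, w in the log-linear setting that Aim 3 names, makes both the power and the labels correct.

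What remains is missing detail about scale, test, degrees of freedom and contrast, which the statistician can look up in the power-software run. Supplying it would alter no sample size, model, test or result. Anyone interpreting a null moderator finding would go by its confidence interval, not by this sentence. As a guide only, under 1:1 allocation, an even split and complete data, 80% power for a difference in GBP effect at one time point needs about 0.91 SD (N=150) or 1.09 SD (N=106). That illustrates the limits of Aim 3; it does not correct a figure in the plan.
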